9.2 Assessment of Causality

The likely relationship of each adverse event to the investigational medical device will be assessed according to the definitions below:

9.2.1 Not related

Is defined as an AE which is not related to the use of the investigational medical device.

9.2.2 Unlikely related

The relationship with the use of the device seems not relevant and/or the event can be reasonably explained by another cause, but additional information may be obtained.

9.2.3 Possibly related

Is defined as an AE which might be due to the use of the investigational device. An alternative explanation (e.g., concomitant drug(s), concomitant disease(s)) is inconclusive. The relationship in time is reasonable; therefore, the causal relationship cannot be excluded.

9.2.4 Probably related

The relationship with the use of the investigational device seems relevant and/or the event cannot reasonably be explained by another cause, but additional information may be obtained.

9.2.5 Related

Data demonstrating clear evidence for a causal relationship (i.e., a clinical event, including laboratory test abnormality, occurring in a plausible time relationship to the investigational medical device, which cannot be explained by concurrent disease or other factors.)

9.3 Adverse Event Reporting Requirements

9.3.1 Investigator Reporting Requirements

All AEs, regardless of seriousness, severity, or presumed relationship to study therapy, must be recorded using medical terminology in the source document and in the eCRF. Whenever possible, diagnoses should be given when signs and symptoms are due to a common etiology (e.g., cough, runny nose, sneezing, sore throat, and head congestion should be reported as "upper respiratory infection"). Investigators must record in the eCRF their opinion concerning the relationship of the AE to study therapy. All measures required for AE management must be recorded in the source document and reported according to Endotronix instructions.

All events will be classified per Adverse Event definitions as documented in Appendix 14.7. Additionally, the date of the event, seriousness criteria and outcome should also be recorded.

Laboratory and clinical parameters will be followed to evaluate the safety and performance of the Cordella PA Sensor System; these include adverse event reporting and monitoring, routine clinical laboratory tests (hematology, biochemistry, and urinalysis), vital signs, review of concomitant medications and echocardiogram.

It is the responsibility of the investigators to inform their IRB/IEC of adverse events as required by their local IRB procedures.

Investigators must notify Endotronix (or designee) within 24 hours of discovering any Unanticipated Adverse Device Effects (UADE)/ Unanticipated Serious Adverse Device Effect (USADE). Investigators are required to submit a report of a UADE/ USADE to the reviewing IRB/ IEC as soon as possible, but in no event later than 10 working days after the investigator first learns of the event. UADEs/USADEs must be documented on the appropriate eCRF.

9.3.2 Regulatory Reporting Requirements

UADE/ USADE:

Endotronix's evaluation of the UADE/ USADE must be reported to the FDA/CAs, all reviewing IRBs/IECs, and participating investigators within 10 working days of knowledge of the event by Endotronix. All UADE/ USADEs will be reported to the FDA/CAs according to regulatory reporting requirements found in CFR 812.46 (US) and MDCG 2020-10/1 under Directive Regulation 2017/ 745 on Medical Device Regulations (MDR) (EU). Contacts for SAE/ UADE/ USADE receipt can be found on the Endotronix/Medical Monitor Contact Information page in the Site File.

AEs/ DDs

Endotronix Inc. is required to expedite to worldwide regulatory authorities reports of AEs and DDs as applicable for each region and in line with the relevant legislation including Safety 21CFR 812.3, CFR 812.46 (US) as well as in MDCG 2020-10/1 under Directive Regulation 2017/745 on MDR (EU).

All investigators will receive a safety letter notifying them of relevant reports. In accordance with the applicable national regulations, Endotronix or designee will notify the relevant IRBs/ IECs of applicable reports as individual notifications or through a periodic line listing as defined in the region's applicable Safety Plan.

Endotronix or its designee will submit to the regulatory authorities all safety updates and periodic reports, as required by applicable regulatory requirements.

Endotronix authorized a CRO to perform the processing (receipt/triage/reporting) of SAEs within this clinical trial. The responsible vigilance contact person is:

[name], Safety Projects Manager,
Syneos Health

Email: [contact]

Details and Instructions on the procedures for the documentation, evaluation and reporting of SAEs occurring in this clinical trial to the German Federal Institute for Drugs and Medical Devices (BfArM) can be found on www.bfarm.de and in the study specific Safety Management Plan.

9.3.3 Contacting Endotronix Regarding Safety

Contacts for SAE/ USADE receipt can be found on the Sponsor/Medical Monitor Contact Information page in the Site File.

9.4 Device/System-Related Complication (DSRC)

Any suspected Cordella PA Sensor System malfunction will be reported to Endotronix and recorded on the eCRF. Any potentially affected component(s) will be returned to Endotronix for evaluation upon request by Endotronix. A DSRC is defined as an adverse event that is, or is possibly, related to the device/system (Cordella PA Sensor System or electronic components) and is either treated invasively (other than intramuscular medication or diagnostic RHC) or results in patient death or explant of the device.

Pressure Sensor Failure is assumed when the sensor malfunctions and no readings can be obtained.

All attempts to troubleshoot (including recalibration) should be exhausted including ruling out any problems with the electronic components, prior to determining that a Pressure Sensor Failure has occurred.

9.5 Study Implant Card

As the subjects are not under 24-hour supervision of the Investigator or site staff, they must be provided with a "study/implant card" indicating the following:

- Investigational device name/model
- Investigational device identifiers (serial numbers, etc....)
- Study number
- Investigator's name
- 24-hour emergency contact number

- Warnings or precautions
- Expected lifetime of the investigational device
- Any other information to ensure safe use of the investigational device

10 STATISTICAL CONSIDERATIONS

10.1 General Statistical Considerations

All data collected in this study will be documented using summary tables and subject data listings. For categorical variables, frequencies and percentages will be presented. For continuous variables, descriptive statistics (n, mean, standard deviation, median, minimum and maximum) will be presented.

Demographic data, including sex, gender, race, age, weight, height, race, ethnicity, BMI, and screening assessments (e.g., primary cardiac diagnosis, previous cardiac history, duration of HF, number of hospitalizations in past year for cardiac) will be summarized using frequencies and percentages, or descriptive statistics, as applicable.

Any deviations from the planned statistical analyses will be reported with proper justification as a protocol deviation.

Statistical analysis will be performed using SAS version 9.3 or higher.

10.2 Analysis Population

The focus of analyses will be on treated subjects from Cohort #2 and #3 (previously enrolled **Treatment Arm** subjects and Newly Enrolled subjects). Unless otherwise specified, the sets defined below are based only on these two treated cohorts.

10.2.1 Enrolled Set

The Enrolled Set will include all subjects enrolled from Cohort #2 and #3. Screen failures are not entered into the database and are therefore not included in this set.

10.2.2 Intent-to-Treat Population (ITT)

The Intent-to-Treat Population (ITT) will include all enrolled subjects intended to receive the Cordella PA Sensor who entered the Cath Lab, including those in whom Implant Procedure is not attempted for whatever reason (e.g., Cordella PA Sensor Implant cannot be performed due to anatomical reasons) from Cohort #2 and #3. Subjects in this population in whom the Cordella PA Sensor Implant is not attempted will be followed through 30 days for safety purposes. The ITT will be used for all analyses of safety endpoints. Effectiveness analysis will not be performed on the ITT population.

10.2.3 Modified Intent-to-Treat Population (mITT)

The Modified Intent-to-Treat Population (mITT) will include all implanted subjects from Cohort #2 and Cohort #3. All primary and secondary effectiveness analyses will be performed on the mITT.

10.2.4 Per Protocol Population (PP)

The Per Protocol Population (PP) will include all mITT subjects without any major protocol deviations. All primary and secondary safety and effectiveness analyses will be performed in addition on PP population. If PP and mITT populations will be identical, analysis will be performed based on mITT only.

10.2.5 Cohort #1- Previously enrolled Control Arm subjects- Population

This subgroup will include all Cohort #1 (previously enrolled Control Arm) subjects and will be reported separately for all endpoints.

10.3 Primary Efficacy Endpoint and Hypotheses

To meet the objectives of the study, observed event rates in the single arm PROACTIVE-HF should be similar to observed event rates in the treatment arm of CardioMEMS studies. Furthermore, observed event rates in the single arm PROACTIVE-HF should be lower than observed event rates in the control arm of CardioMEMS studies.

Thus, we set the performance goal (PG) as the LOWER of 1) the meta-analysis upper bound confidence interval of CardioMEMS treated patients, and 2) the meta-analysis estimate of CardioMEMS control patients, further adjusted down by potential impact of SGLT2i.

Furthermore, we also require that the single arm PROACTIVE-HF observed event rate is LOWER than both 1) the meta-analysis estimate of CardioMEMS treatment patients, and 2) the lowest observed event rates of CardioMEMS control patients, further adjusted down by potential impact of SGLT2i.

The primary endpoint will be the 6 month incidence of HF related Hospitalizations (HFH) or all-cause mortality compared to a PG.

Meta-analysis of treatment and control event rates were considered in determining the Primary Endpoint PG. Meta-analyses were based on a random effects meta-analysis for the log-transformed

incidence rate fit via restricted maximum likelihood. Results are back transformed to the rate scale. Calculations were performed in R version 3.6.3 with the “metafor” package.

The mean 6 month event rate from the meta-analysis of prior control studies is 0.46, or 0.43 on an adjusted basis to account for SGLT2i inclusion in the guidelines^a. A 6 month event rate of 0.43 also represents a value just below both the highest event rate observed across the CardioMEMS treatment studies (0.44 in MEMS-HF) and the upper bound of the overall meta-analytic treatment estimate (0.44). Taking the totality of results from the meta-analysis of active treatment trials, individual results of active treatment trials, as well as the meta-analysis of control trials, we set the primary endpoint performance goal (PG₆) at 0.43.

Furthermore, the mean 6 month event rate from the meta-analysis of prior treatment studies is 0.38, with both the CHAMPION (0.37) and GUIDE-HF (0.31, NYHA class III) treatment groups with event rates lower than the mean. The lowest 6 month event rate across CardioMEMS control studies of 0.39 occurred in GUIDE-HF (NYHA class III), where modest use of SGLT2i occurred during the trial. We conservatively adjust this lowest observed control event rate down to 0.37 to account for increased SGLT2i utilization.

The table below outlines the data sources used to derive a PG for this endpoint.

Since patient level data was not available and summary data was limited in scope, analysis was based on the numbers of events reported from each study and the number of enrolled subjects was for denominator, assuming all subjects were followed for the corresponding time period. Accordingly, the estimates are likely conservative underestimates of true rates since complete follow-up on all subjects was unlikely.

For studies reporting only 12 month rates, estimates of 6 month rates were estimated via an exponential distribution. For example, for a study with a reported 12 month rate, r_{12} , we calculated the 6 month rate, r_6 , as:

$$r_6 = 1 - \exp(\log_n(1 - r_{12})/2)$$

where the division by two (2) accounts for a calculation of the rate for half the follow-up time (i.e. a linearized rate). When possible, events of each type (HF related hospitalization and death) were

^a Adjustment applied assuming 50% use of SGLT2i at the average hazard ratio observed across EMPEROR Preserved, EMPEROR REDUCED, DAPA-HF for NYHA III subjects.

calculated separately and summed to produce the composite event counts and the corresponding composite rate. Rates are calculated as numbers of events over numbers of subjects.

Active Treatment - updated 6 Month Rates with calculation details

Study/Publication	Number of Subjects ¹	Events	Rate ²	Details
CHAMPION ¹⁹	270	99	0.37	
 - 6 month HFH rate reported as 0.31, yielding approx. 84 events - 15 deaths reported - Adding calculated 6 month HFH events and deaths yields 99 events
MEMS PAS ⁴⁴	1200	493	0.41	
 - 6 month rate calculated via reported 12 month rate of 0.54 - Calculated 6 month HFH rate of 0.32, yielding 386 events - 107 deaths reported - Adding calculated 6 month HFH events and deaths yields 493 events
MEMS-HF ⁴⁶	234	102	0.44	
 - 6 month HFH calculated via reported 12 month rate of 0.60 - Calculated 6 month HFH rate of 0.37, yielding 86 events - 16 deaths reported - Adding calculated 6 month HFH and deaths yields 102 events
GUIDE-HF ⁵² – NYHA class III only	322	100	0.31	
 - Reported 12 month rate of 0.431/0.089 for HFH/D, for composite of 0.52. - Assuming exponential rate, calculated 6 month rate (events) is 0.31 (100) - Events calculated as 322 subjects x 0.31
Estimate (CI)			0.38 (0.33, 0.44)	

¹ Numbers of subjects are those treated subjects estimated to be followed for 6 month events.

² Estimates for events are based on either reported results or are estimated from published figures. For studies reporting 12 month results, 6 month rates were estimated based on exponential rates.

Altogether, for study success, *the upper confidence bound of the observed event rate* for the planned study must be less than the PG_6 (0.43) and the observed event rate must be less than 0.37. Evaluating the upper bound of the confidence interval for the rate ensures that 1) the observed rate will be comparable to prior studies of active treatment (highest observed value = 0.44), 2) the observed rate will be less than the meta-analytic value derived from prior studies of treatment and control, and 3) the observed rate will be less than the lowest rate observed in the control studies (GUIDE HF). The added requirement for the observed event rate to be less than 0.37 provides further assurance that results are comparable to studies of prior CardioMEMS treatment.

The assumed PROACTIVE-HF population event rate is expected to be 0.34. This assumed event rate is lower than all prior active CardioMEMS treatment rates except for GUIDE-HF. While the

contemporary GUIDE-HF study observed an event rate of 0.31 (NYHA Class III), PROACTIVE-HF has higher NTproBNP thresholds than the GUIDE-HF cohort and we expect subjects with higher NTproBNP levels to more closely align with subjects with a recent hospitalization, which have higher event rates.

The mathematical statement of the null and alternative hypothesis is as follows:

$$H_0: r_6 \geq PG_6$$

$$H_A: r_6 < PG_6$$

where r_6 is the 6 month rate of primary endpoint events and PG_6 is the performance goal. A value of 0.43 will be used for the goal. The null hypothesis will be rejected if the upper confidence bound for the rate is less than the performance goal, or equivalently, that the corresponding p-value from the hypothesis test is less than 0.025. An observed rate of less than 0.37 and rejection of the null hypothesis indicate that the observed rate is statistically less than the performance goal, indicating clinically acceptable results and study success. Analysis will be based on a Poisson regression approach for the number of events, with the log follow-up time as an offset term. Sensitivity analyses using a negative binomial approach to capture within-subject correlation will be performed.

The study will implant 450 subjects (combined in Cohort #2 and Cohort #3) leading to an expected evaluable cohort of 406 subjects. With a goal of 0.43 and a one-sided 0.025 alpha level, the study will have greater than 80% power assuming a population treatment rate of 0.34. Calculations are based on a one-sample Poisson rate test and were performed with PASS 2021.

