10.4 Additional Secondary Efficacy Endpoints

The first secondary efficacy endpoint is incidence of HF Hospitalizations or all-cause mortality at 12 months compared to a PG.

The mean 12 month event rate from the meta-analysis of prior control studies is 0.75, or 0.70 on an adjusted basis to account for SGLT-2i inclusion in the guidelines^b. A 12 month event rate of 0.70 represents a value just below the highest event rate observed across the CardioMEMS treatment studies (0.73 in MEMS-HF) and the upper bound of the overall meta-analytic treatment estimate (0.74). Taking the totality of results from the meta-analysis of active treatment trials, individual

^b Adjustment applied assuming 50% use of SGLT2i at the average hazard ratio observed across EMPEROR Preserved, EMPEROR REDUCED, DAPA-HF for NYHA III subjects.

results of active treatment trials, as well as the meta-analysis of control trials, we set the secondary endpoint performance goal (PG₁₂) at 0.70.

Furthermore, the mean 12 month event rate from the meta-analysis of prior treatment studies is 0.64, with both the CHAMPION (0.6) and GUIDE-HF (0.52, NYHA class III) treatment groups with event rates lower than the mean. The lowest 12 month event rate across CardioMEMS control studies of 0.63 occurred in GUIDE-HF (NYHA class III only), where modest use of SGLT2i occurred during the trial. We conservatively adjust this lowest observed control event rate down to 0.59 to account for increased SGLT2i utilization.

The table below outlines the data sources used to derive a PG for this endpoint.

Active Treatment - updated 12 Month Rates with calculation details

Study/Publication	Number of Subjects ¹	Events	Rate ²	Details
CHAMPION ⁵³	270	162	0.60	- HFH rate of 0.46, yielding approx. 124 events - Mortality rate of 0.14, yielding approx. 38 events - Total events = 124 + 38
MEMS PAS ⁴⁴	1200	840	0.70	- HFH rate of 0.54, yielding 648 events - Mortality rate of 0.16, yielding 192 events - Total events = 648 + 192
MEMS-HF ⁴⁶	234	171	0.73	- HFH rate of 0.60, yielding 140 events - Mortality rate of 0.13, yielding approx. 30 events - Total events = 140 + 31
GUIDE-HF ⁵¹ – NYHA class III only	322	167	0.52	- - HFH rate of 0.431 + plus death rate of 0.0897 - Composite rate = 0.52 - Total events = 322 subjects x 0.52
Estimate CI			0.64 (0.55, 074)	

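### A cumulative-probability formula converts 12-month event-count rates to 6 months, and the roughly 61% six-month share implied by the 0.43 goal is neither stated nor justified

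*Protocol*

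**What the plan says.** Protocol 10.3 sets the 6-month goal (PG6) by a rule with two limbs: "we set the performance goal (PG) as the LOWER of 1) the meta-analysis upper bound confidence interval of CardioMEMS treated patients", and "the meta-analysis estimate of CardioMEMS control patients, further adjusted down by potential impact of SGLT2i". The treated upper bound is 0.44. For controls, "The mean 6 month event rate from the meta-analysis of prior control studies is 0.46, or 0.43 on an adjusted basis". The control limb is the lower, so PG6 = 0.43. Protocol 10.4 gives the 12-month counterpart: "The mean 12 month event rate from the meta-analysis of prior control studies is 0.75, or 0.70 on an adjusted basis". A second condition caps the observed 6-month rate at 0.37. The cap comes from the GUIDE-HF NYHA III control rate (0.63 at 12 months, 0.39 at 6 months) after an SGLT2i adjustment.

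Where a study reported only 12-month results, both documents use r6 = 1 − exp(ln(1 − r12)/2) under an exponential assumption. The Protocol explains it as "where the division by two (2) accounts for a calculation of the rate for half the follow-up time (i.e. a linearized rate". SAP 2.4.1 has the same formula without the remark about linearizing.

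On the scale of the rates, Protocol 10.3 says "Rates are calculated as numbers of events over numbers of subjects". The MEMS PAS row of the 12-month table confirms this: "HFH rate of 0.54, yielding 648 events", in 1,200 subjects. For the trial itself, "Analysis will be based on a Poisson regression approach for the number of events, with the log follow-up time as an offset term". Protocol 10.3 also presents the upper-bound criterion as guaranteeing an observed rate below the lowest control-study rate, that of GUIDE-HF.

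**The concern.** The formula halves a cumulative hazard and is correct when r12 is the probability of at least one event by 12 months. Here r12 is a mean count per subject. For a mean count under a constant rate, half the time gives half the events. The formula always gives more than that, and it is undefined above one event per subject.

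This matters because the trial has no concurrent comparator: PG6 and the 0.37 cap carry the efficacy claim. A conversion that puts too many events in the first six months raises the benchmark and makes it easier to pass. The plan also never says what fraction of 12-month events it places in months 1 to 6, so a reader cannot judge whether the 6-month and 12-month goals agree.

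**Working it through.** **1. The plan's figures reproduce.** With r6 = 1 − √(1 − r12), from the inputs in Protocol 10.3 and 10.4:

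| Input | r12 | Formula | r12/2 | Ratio |
|---|---|---|---|---|
| MEMS PAS, HF hospitalization (HFH) | 0.54 | 0.322 | 0.270 | 1.19 |
| MEMS-HF, HFH | 0.60 | 0.368 | 0.300 | 1.23 |
| GUIDE-HF treated, composite | 0.52 | 0.307 | 0.260 | 1.18 |
| GUIDE-HF control | 0.63 | 0.392 | 0.315 | 1.24 |

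The formula column matches the printed 0.32, 0.37, 0.31 and 0.39. A REML random-effects pool of log rates (variance 1/events; 99, 493, 102 and 100 events in 270, 1,200, 234 and 322 subjects) gives 0.382 (0.333, 0.438), against the printed 0.38 (0.33, 0.44).

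**2. The formula does not suit counts.** With a constant rate λ per year, expected events per subject are λ at 12 months and λ/2 at 6. The formula is also not additive. For GUIDE-HF the composite gives 0.307, but the printed components (0.431 and 0.089) give 0.246 + 0.046 = 0.291 (difference from the sum is rounding). Halving gives 0.26 either way.

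**3. Effect on the treated limb.**
- GUIDE-HF by component (93.8 events): 0.375 (0.318, 0.443), so little change in the bound.
- Converted inputs halved, CHAMPION and the printed 6-month deaths kept (99, 431, 86.2, 83.7 events): 0.338 (0.291, 0.393).
- All four 12-month composites multiplied by 0.611: 0.390 (0.337, 0.452).

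**4. The implied share on the binding limb.** 0.43/0.70 = 0.614. Rounding allows 0.425/0.705 = 0.603 to 0.435/0.695 = 0.626. This is a quotient of two pooled figures, not a demonstrated output of the formula: applied to the pooled control mean of 0.75, the formula gives 1 − √0.25 = 0.50, not 0.46.

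**5. Evidence in the documents on the share.**
- CHAMPION composite, not converted: 99/162 = 0.61. The two counts come from different sources.
- CHAMPION HFH (0.46 at 12 months): the formula gives 0.265 and r12/2 gives 0.23, against 0.31 reported. Neither reproduces it.
- Printed deaths in CHAMPION, MEMS PAS and MEMS-HF: (15 + 107 + 16)/(38 + 192 + 31) = 138/261 = 0.53. Deaths are 261 of 1,173 events (22%) in those studies.

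**6. The assurance about the lowest control rate.** For PG6 = 0.43, n = 406 and one-sided 0.025, the largest passing count is 148, a rate of 148/406 = 0.3645, so the 0.37 cap does not bind. The GUIDE-HF control rate at 6 months is 0.63 × share. A passing rate is certain to lie below it only if the share exceeds 0.3645/0.63 = 0.58. For the SGLT2i-adjusted 0.59 it is 0.3645/0.59 = 0.62. A constant rate corresponds to 0.50.

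**The case against.** The strongest reply is that the formula has not been shown to produce the 0.43. That stands. No control table is printed, and only the GUIDE-HF control rate can be traced to the formula. If there were two equally weighted control studies (an assumption), the other would be 0.75²/0.63 = 0.893 at 12 months and 0.46²/0.39 = 0.543 at 6. The formula would turn 0.893 into 0.67.

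Second, the one study with unconverted data at both times has a share of 0.61, as the printed goal implies, and halving fits its HFH rate worse than the formula does. That stands too, and it rules out r12/2 as a default.

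Third, the source rates divide by all enrolled subjects, whereas the trial divides by exposure time, and the Protocol says its estimates are probably too low for that reason. This offsets part of the difference. If mean follow-up were 95% or 90% (assumed), the halved-input treated bound of 0.393 would become 0.41 or 0.44.

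Fourth, the word linearized can be read as describing the halving of ln(1 − r12), which is linear in time. That explains the label but does not make the formula suit event counts.

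Fifth, the 12-month criteria (0.70 and 0.59) use unconverted rates. They give some protection, but that test is secondary and is reached only after the primary null is rejected.

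**Conclusion.** The derivation is wrong as written. A formula for probabilities is applied to events-per-subject rates, it overstates a constant-rate conversion by 18% to 24%, and the Protocol's label does not describe it. It affects three of the four treated studies and at least the GUIDE-HF control rate behind the cap. The share of about 61% implied by PG6 and the 12-month goal is unstated and unjustified.

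A reader might infer that 0.43 is too high because of the formula, or that it should be about 0.35 (0.70 × 0.50). The documents support neither. The 0.35 figure is a conditional lower extreme: it needs a constant rate, every control input converted and complete follow-up in the source studies. The evidence on the share is mixed, with CHAMPION at 0.61, deaths at 0.53 and incomplete follow-up working in the plan's favour.

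What can be said firmly is that the assurance about the lowest control rate is conditional. It holds if the GUIDE-HF control share is above about 0.58, given 406 evaluable subjects, and the plan gives no basis for that.

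**What to change.** Keep 0.43, 0.37, the primary test and the sample size. Correct their support in Protocol 10.3 and SAP 2.4.1:

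1. Replace the formula, and the Protocol's linearized label, with reported 6-month counts where they exist. Otherwise use a stated and justified share of 12-month events in months 1 to 6. Show r12/2 only as the constant-rate sensitivity case.
2. Convert GUIDE-HF by component, as for the other studies.
3. Print the control-study inputs and rerun both meta-analyses.
4. Report both limbs of PG6 and the cap on three bases, with the follow-up assumption stated. From the figures available now:

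| Basis | Treated upper bound | Control limb | Cap |
|---|---|---|---|
| As printed | 0.44 | 0.43 | 0.37 |
| Share 0.50 | 0.39 (converted inputs halved) | 0.35 (lower extreme) | 0.63 × 0.50 × 0.37/0.39 = 0.30 |
| Share 0.611 | 0.45 | 0.43 | 0.63 × 0.611 × 0.37/0.39 = 0.365 |

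5. Reword the assurance about the lowest control rate as conditional on the share.

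The cost is two rerun meta-analyses, some text and one table. Power is unchanged (81% at 0.34 with n = 406). The downside is a less favourable description of how well the benchmark is supported.
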